4.4.1.3 Urinalysis

Urine positive for protein or blood will have a microscopic examination performed. Further investigation may be undertaken at the discretion of the investigator. Blood in urine due to

menses may be marked as such and notated as ‘not clinically significant’ (NCS) without further microscopic examination.

4.4.1.4 Serum pregnancy test

Female volunteers of childbearing potential will have a serum pregnancy test. The serum pregnancy test can be collected with the same sample as the blood chemistry. If the result is positive, the volunteer will not be allowed to proceed in the trial.

4.4.2 Brief physical exam

The brief physical examination will be conducted at the times specified in the study plan ([Table 1](#)) and will include an assessment of the following:

- General appearance
- Cardiovascular
- Lungs
- Abdomen

Brief physical examination data to be recorded on the CRF will include: 1) normal/abnormal and 2) a description of any abnormalities

4.4.3 Vital signs

For timing of individual measurements refer to the study plan ([Table 1](#)).

Vital signs consist of a sitting heart rate, sitting blood pressure, and oral temperature.

Oral temperature will be measured in °C at screening and Days –1A, -1B, and -1C only.

AstraZeneca will provide the investigator reference range values for each vital sign measurement required by the protocol

4.4.3.1 Blood pressure and heart rate

Heart rate and blood pressure will be measured after the volunteer has been seated for at least 5 minutes. Heart rate will be determined by palpation of the radial pulse for a period of 30 seconds and then multiplied by two, or as measured by an automatic device (e.g. Dinamap®). Blood pressure will be measured using a blood pressure device with an appropriate cuff size. The same device and same arm will be used for each measurement.

4.5 Genetic measurements and co-variables

Consent for genetic research will be obtained on a separate consent form. Refusal to provide such consent is an exclusion criterion and will preclude participation in the main pharmacokinetic study if not provided. The blood samples obtained under this consent will be

used to study the genes implicated in the ADME of statins. DNA samples will not be used in other types of genetic or non-genetic research either as test or control specimens.

4.5.1 Collection of samples for genetic research

Blood samples will be obtained from each volunteer and used to prepare DNA samples. A record of the date of the volunteer consent to the genetic research and the date of the blood sample collection will be recorded in the appropriate section of the CRF.

4.5.1.1 Processing of genetic samples

Approximately 9 mL of blood will be collected from consenting volunteers into ethylenediaminetetraacetic acid (EDTA) coated polypropylene tubes at the time indicated in the protocol study plan (Table 1). The blood should be mixed by gentle inversion of the tube.

Glass tubes must not be used as they may break during transport.

Heparin must not be used as an anticoagulant as it may interfere with downstream genotyping methodology.

After collection, blood samples must be stored appropriately at the site of collection and transported to the AstraZeneca Clinical Genotyping Laboratory as soon as possible.

The samples will be frozen immediately after collection and may be stored at -20°C or -70°C . The samples should be kept frozen until analyzed.

If blood samples are to be stored at -20°C , non-frost free freezers must be used to prevent repeated freeze-thaw of blood, which may reduce yield and quality of the DNA, obtained.

Samples must not be thawed and then re-frozen at any point.

4.5.1.2 Labeling of genetic samples

Collection tubes will be labeled with the following information:

- Genetic sample
- Date of sample
- Study number
- Randomization/Subject number

4.5.1.3 Shipping of genetic samples

For safety reasons, all blood samples must be contained. Standard procedures for transporting biological samples as defined by the courier and in compliance with local regulations will be followed.

Blood samples for genetic analysis collected from each consenting volunteer will be shipped to AstraZeneca Clinical Genotyping Laboratory. The samples must be shipped frozen in dry ice via expedited overnight delivery. The samples must be packed securely to avoid damage during transit, must be double bagged to contain leaks, and will be packed with a sufficient quantity of dry ice to ensure they remain frozen for a minimum of 72 hours. Allowance should be made for possible delay of shipment.

All applicable shipping regulations must be followed. Documentation sufficient to identify each sample (i.e., list of subject identification numbers) must be included in the shipment. The AstraZeneca contact must be notified by telephone or fax when the samples are shipped. All shipping details, including study ID, number of samples, list of sample ID's, courier name, airway bill number, and date of shipment must be provided.

Samples must be shipped on Mondays or Tuesdays only to ensure delivery before the weekend. Do not ship on or the day before a legal holiday.

Samples will be sent to the following address:

4.5.1.4 Storage and coding of DNA samples

The processes adopted for the coding and storage of samples for genetic analysis are important to maintain volunteer confidentiality.

For all samples, irrespective of the type of coding used, the DNA will be extracted from the blood sample. The DNA sample will be assigned a unique number replacing the information on the sample tube. Thereafter, the DNA sample will be identifiable by the unique DNA number only. The DNA number will be used to identify the sample and corresponding data at the AstraZeneca genetics laboratories, or at the designated contract laboratory. No personal

details identifying the individual will be available to any AstraZeneca employee working with the DNA.

The blood samples and data for genetic analysis in this study will be coded. Each blood sample will be labeled with the study number and subject number. Only the investigator will be able to link the blood sample to the individual volunteer. The sample and data will not be labeled with a personal identifier. The link between the subject enrollment/randomization code and the DNA number will be maintained.

This link file and any corresponding genetic data will be stored in a secure environment, with restricted access within the

. The link will be used to identify the relevant DNA samples for analysis, facilitate correlation of genotypic results with clinical data, allow regulatory audit and to trace samples for destruction in the case of withdrawal of consent. Access to the link file will require written authorization from the Project Team Leader.

All DNA samples will be stored under secure conditions with restricted access at AstraZeneca. The blood, DNA samples or data derived from the samples may be made available to groups or organizations working with AstraZeneca on this study or as part of the development drug project. However, the samples and any results will remain the property of AstraZeneca at all times. AstraZeneca will not give blood, DNA samples or data derived from the samples to any other parties, except as required by law.

Samples will be stored for a maximum of 15 years, from the date of completion of the study, after which they will be destroyed.

DNA is a finite resource that is used up during analyses. Samples will be stored and used until no further analyses are possible. Further samples will not be acquired from volunteers.

4.5.1.5 Summary of genetic assessments and analysis

The purpose of the genetic research is to generate data for use in future retrospective analyses. Future analyses will explore genetic factors that may influence the disposition, efficacy, safety and tolerability to rosuvastatin. The results of the genetic research will not form part of the clinical study report for this study, but will be recorded and reported separately.

4.6 Volume of blood sampling

The total volume of blood that will be drawn from each volunteer in this study is as follows:

Table 5 Volume of blood to be drawn from each volunteer

Assessment		Sample volume (mL)	n of samples	Total volume (mL)
Blood sampling for rosuvastatin		4 mL	19	95 mL
Blood sampling for atorvastatin		7 mL	19	133 mL
Blood sampling for simvastatin		7 mL	16	112 mL
Lipid profile		10 mL	1	10 mL
Genetic sample		9 mL	1	9 mL
Safety	Serology	10 mL	1	10 mL
	Clinical chemistry/serum pregnancy	10 mL	5	50 mL
	Hematology	10 mL	5	50 mL
Total			67	469 mL

4.7 Adverse Events

The methods for collecting adverse events are described below.

4.7.1 Adverse Events

4.7.1.1 Definitions

The definitions of adverse events (AEs), serious adverse events (SAEs) and other significant adverse events (OAEs) are given below. It is of the utmost importance that all staff involved in the study is familiar with the content of this section. The principal investigator is responsible for ensuring this.

Adverse event

An adverse event is the development of an undesirable medical condition or the deterioration of a pre-existing medical condition following or during exposure to a pharmaceutical product, whether or not considered causally related to the product. An undesirable medical condition can be symptoms (e.g., nausea, chest pain), signs (e.g., tachycardia, enlarged liver) or the abnormal results of an investigation (e.g., laboratory findings, electrocardiogram). In clinical studies, an AE can include an undesirable medical condition occurring at any time, including run-in or washout periods, even if no study treatment has been administered.

Serious adverse event

A serious adverse event is an AE occurring during any study phase (i.e., run-in, treatment, washout, follow-up), and at any dose of the investigational product, comparator or placebo, that fulfills one or more of the following criteria:

- Results in death
- Is immediately life-threatening
- Requires in-patient hospitalization or prolongation of existing hospitalization
- Results in persistent or significant disability or incapacity
- Is a congenital abnormality or birth defect
- Is an important medical event that may jeopardize the volunteer or may require medical intervention to prevent one of the outcomes listed above.

The causality of SAEs (i.e., their relationship to study treatment) will be assessed by the investigator(s), who in completing the relevant case report form must answer “yes” or “no” to the question “Do you consider that there is a reasonable possibility that the event may have been caused by any of the following – study medication – other medication?” For further guidance on the definition of a SAE and a guide to the interpretation of the causality question, see [Appendix B](#) to the Clinical Pharmacology Study Protocol.

Note that SAEs that could be associated with any study procedure should also be reported. For such events the causal relationship is implied as “yes”.

Other Significant Adverse Events (OAE)

OAEs will be identified by the Study Delivery Team Physician in consultation with the appropriate Global Drug Safety Physician during the evaluation of safety data for the Clinical Study Report. Significant adverse events of particular clinical importance, other than SAEs and those AEs leading to discontinuation of the volunteer from study treatment, will be classified as OAEs. Examples of these are marked hematological and other laboratory abnormalities, and certain events that lead to intervention (other than those already classified as serious), dose reduction or significant additional treatment. For each OAE, a narrative may be written and included in the Clinical Study Report.

4.7.1.2 Recording of adverse events

Adverse events will be collected beginning Day –1A through the final assessment of the final treatment period. SAEs will be collected from the time the informed consent is signed through final assessment of the final treatment period.

The following will be recorded for each AE:

- Start date
- Stop date
- Maximum intensity

- Action taken
- Outcome
- Causality (yes or no)
- Whether conditions constitute and SAE

The intensity rating is defined as:

- mild (awareness of sign or symptom, but easily tolerated)
- moderate (discomfort sufficient to cause interference with normal activities)
- severe (incapacitating, with inability to perform normal activities)

It is important to distinguish between serious and severe AEs. Severity is a measure of intensity whereas seriousness is defined by the criteria in Section 4.7.1.1. An AE of severe intensity need not necessarily be considered serious. For example, nausea that persists for several hours may be considered severe nausea, but not a SAE. On the other hand, a stroke that results in only a limited degree of disability may be considered a mild stroke but would be a SAE.

Should a pregnancy occur, it must be reported in accordance with the procedures described in Section 8.3. Pregnancy in itself is not regarded as an AE unless there is a suspicion that an investigational product may have interfered with the effectiveness of a contraceptive medication.

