1.1 Background

1.1.1 Clinical pharmacology of rosuvastatin

Rosuvastatin has been studied in North American, European, and Asian volunteers. In clinical pharmacology studies in volunteers, peak plasma concentrations of rosuvastatin are reached 3 to 5 hours following oral dosing. Both C_{max} and area under the concentration curve from zero to infinity (AUC) increase in approximate proportion to rosuvastatin dose. The absolute bioavailability of rosuvastatin in Caucasian and Japanese volunteers is approximately 20% and 29% respectively.

Administration of rosuvastatin with food decreased the rate of drug absorption by 20% as assessed by C_{max} but there was no effect on the extent of absorption as assessed by AUC. Plasma concentrations of rosuvastatin do not differ following evening or morning drug administration. Significant LDL-C reductions are seen when rosuvastatin is given with or without food, and regardless of the time of day of drug administration.

Mean volume of distribution at steady state of rosuvastatin is approximately 134 litres and 69 litres in Caucasian and Japanese volunteers respectively. Rosuvastatin is approximately 88% bound to plasma proteins, mostly albumin. This binding is reversible and independent of plasma concentrations.

Rosuvastatin is not extensively metabolised; approximately 10% of a radiolabeled dose is recovered as metabolite. The major metabolite is N-desmethyl rosuvastatin, which is formed principally by cytochrome P450 2C9. In vitro studies have demonstrated that N-desmethyl rosuvastatin has approximately one-sixth to one-half the HMG-CoA reductase inhibitory activity of rosuvastatin. Overall, greater than 90% of plasma HMG-CoA reductase inhibitory activity is accounted for by rosuvastatin.

Following oral administration, rosuvastatin and its metabolites are primarily excreted in the faeces (90%). The terminal elimination half-life ($t_{1/2\lambda z}$) of rosuvastatin is approximately 19 hours.

After an intravenous dose, approximately 28% of total body clearance was via the renal route, and 72% by the hepatic route.

In vitro and in vivo data indicate that rosuvastatin clearance is not dependent on metabolism by cytochromes P450 3A4 and 2C9 to a clinically significant extent. Rosuvastatin also does not interact to a clinically significant extent with the p-glycoprotein transporter.

Please refer to the investigator's brochure (IB) for additional information.

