1.1.4 Safety of rosuvastatin

Review of adverse event data show that rosuvastatin is well tolerated. The overall frequency of alanine aminotransferase (ALT) elevations is low. Clinically significant ALT elevations (>3 x the upper limit of normal [ULN] on two or more occasions) are uncommon and for the most part resolve with either continued therapy with or without dose reduction or after an interruption of treatment. No cases of irreversible liver injury secondary to rosuvastatin therapy have been identified.

Muscle-related findings (i.e., creatine kinase [CK] increases, myalgia, and myopathy) are a well-recognized complication of statin therapy. As with other HMG-CoA reductase inhibitors, effects on skeletal muscle, e.g. uncomplicated myalgia, myopathy and, rarely rhabdomyolysis have been reported in patients treated with rosuvastatin. The reporting rate for rhabdomyolysis in post-marketing use is higher at the highest marketed dose, which is consistent with other HMG-CoA reductase inhibitors.

The analysis of renal data indicates that proteinuria, predominantly tubular in nature, occurs at a low frequency among volunteers receiving rosuvastatin in doses up to and including 40 mg. A low frequency of proteinuria was also observed in volunteers treated with other statins in the rosuvastatin clinical program. The proteinuria seen with rosuvastatin is not associated with clinically significant increases in serum creatinine or worsening renal function. The 40 mg rosuvastatin dose is well tolerated in terms of renal effect with both shorter-term and longer-term treatment.

Please refer to the IB for additional information.

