completion of the final blood sample and all safety assessments are completed on Day 4A. Volunteers taking simvastatin will be discharged after the final blood sample and all safety assessments are completed on Day 3A.

Treatment Period B: After a washout period of at least 7 days, volunteers will return to the CRC for Treatment Period B. Day -1B assessments will be completed as described in the Study Plan ([Table 1](#)). On Day 1B, volunteers will receive a single dose of study drug (according to their Treatment Sequence) under fasting conditions. Blood samples will be taken and volunteers discharged as described in Treatment Period A.

Treatment Period C: After a washout period of at least 7 days, volunteers will return to the CRC for Treatment Period C. Day -1C assessments will be completed as described in the Study Plan ([Table 1](#)). On Day 1C, volunteers will receive a single dose of study drug (according to their Treatment Sequence) under fasting conditions. Blood samples will be taken as described in Treatment Period A. Volunteers will be discharged from the study after completion of the final blood sample and all safety assessments are completed on Day 4C. Volunteers taking simvastatin will be discharged from the study after the final blood sample and all safety assessments are completed on Day 3C.

Figure 1 Study flow chart

[figure not shown]

Table 1 Study Plan

Activity	Screening Period	Treatment Period A					Treatment Period B					Treatment Period C			
		Day -1A	Day 1A	Day 2A 3A	Day 4A		Day -1B	Day 1B	Day 2B 3B	Day 4B		Day -1C	Day 1C	Day 2C 3C	Day 4C
Informed Consent	√														
Genetic Consent ^a	√														
Inclusion / Exclusion	√	√					√					√			
Demographics	√														
Medical / Drug History	√					7					7				
Urine Drug Screen	√	√					√					√			
Complete Physical Exam	√					D					D			√	
Brief Physical Exam ^b		√				A	√				A	√			
Dietary Assessment ^c	√					Y					Y				
Electrocardiogram	√					W					W				
Chemistry/Hematology ^b	√	√				A	√				A	√		√	
Fasting Lipid Profile ^d			√			S					S				
Serology	√					H					H				
Urinalysis ^b	√	√				O	√				O	√		√	
Serum Pregnancy ^b	√	√				U	√				U	√		√	
Vital Signs ^{b,e}	√	√	√	√	√	T	√	√	√	√	T	√	√	√	
Genetic Blood Sample ^a			√												
Administration of Study Drug			√					√					√		

Activity	Screening Period	Treatment Period A				Treatment Period B				Treatment Period C					
		Day -1A	Day 1A	Day 2A 3A	Day 4A	Day -1B	Day 1B	Day 2B 3B	Day 4B	Day -1C	Day 1C	Day 2C 3C	Day 4C		

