Blood Sampling ^f			√	√	√			√	√	√			√	√	√
Adverse Events Concomitant Meds ^g	√	√	√	√	√	√	√	√	√	√	√	√	√	√	√
Discharge ^h					√					√					√

- a. Volunteers declining to participate in the genetic portion of the study may not participate in the main pharmacokinetic study
- b. Clinical assessments scheduled for Day 4 will be on Day 3 for volunteers receiving simvastatin
- c. A 3-day diet diary will be completed and returned to the clinical research center (CRC) for analysis during the screening period
- d. Fasting (10 hours) lipid profile to measure total cholesterol (TC), triglycerides (TG), high density lipoprotein cholesterol (HDL-C) and low density lipoprotein cholesterol (LDL-C)
- e. Vital signs will be taken at screening, Day -1, before dosing on Day 1 and in the mornings on Days 2-4
- f. Serial blood sampling for rosuvastatin and atorvastatin will be done pre-dose (within 30 minutes), and 0.5, 1, 2, 3, 4, 5, 6, 8, 10, 12, 18, 24, 30, 36, 48, 54, 60, and 72 hours post-dose. Serial blood sampling for simvastatin will be done pre-dose (within 30 minutes), and 0.5, 1, 2, 3, 4, 5, 6, 8, 10, 12, 18, 24, 30, 36, and 48 hours post-dose.
- g. Volunteers will continue with study restrictions during the washout periods. Concomitant meds should be cleared by the principal investigator if at all possible and recorded on the case report form (CRF). Adverse events and concomitant medication use should be solicited upon return to the CRC after washout or reported by the volunteer during the washout period and recorded on the appropriate CRF.
- h. Volunteers receiving simvastatin will be discharged after the final blood sample (48 hours post-dose) on Day 3

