8.3 Procedures in case of pregnancy

Pregnancy itself is not regarded as an adverse event unless there is a suspicion that the investigational product under study may have interfered with the effectiveness of a contraceptive medication. However, the outcome of all pregnancies (spontaneous miscarriage, elective termination, normal birth or congenital abnormality) must be followed up and documented even if the volunteer was discontinued from the study.

All reports of congenital abnormalities/birth defects are SAEs. Spontaneous miscarriages should also be reported and handled as SAEs. Elective abortions without complications should not be handled as AEs. All outcomes of pregnancy must be reported to AstraZeneca on the pregnancy outcomes report form.

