enterohepatic recirculation. Mean plasma elimination half-life of atorvastatin in humans is approximately 14 hours, but the half-life of inhibitory activity for HMG-CoA reductase is 20 to 30 hours due to the contribution of active metabolites. Less than 2% of a dose of atorvastatin is recovered in urine following oral administration.

Special Populations

Geriatric: Plasma concentrations of atorvastatin are higher (approximately 40% for C_{max} and 30% for AUC) in healthy elderly subjects (age >65 years) than in young adults. Clinical data suggest a greater degree of LDL-lowering at any dose of drug in the elderly patient population compared to younger adults (see PRECAUTIONS section; Geriatric Use subsection).

Pediatric: Pharmacokinetic data in the pediatric population are not available.

Gender: Plasma concentrations of atorvastatin in women differ from those in men (approximately 20% higher for C_{max} and 10% lower for AUC); however, there is no clinically significant difference in LDL-C reduction with LIPITOR between men and women.

Renal Insufficiency: Renal disease has no influence on the plasma concentrations or LDL-C reduction of atorvastatin; thus, dose adjustment in patients with renal dysfunction is not necessary (see DOSAGE AND ADMINISTRATION).

Hemodialysis: While studies have not been conducted in patients with end-stage renal disease, hemodialysis is not expected to significantly enhance clearance of atorvastatin since the drug is extensively bound to plasma proteins.

Hepatic Insufficiency: In patients with chronic alcoholic liver disease, plasma concentrations of atorvastatin are markedly increased. C_{max} and AUC are each 4-fold greater in patients with Childs-Pugh A disease. C_{max} and AUC are approximately 16-fold and 11-fold increased, respectively, in patients with Childs-Pugh B disease (see CONTRAINDICATIONS).

Clinical Studies

Prevention of Cardiovascular Disease

[figure not shown]

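### Collection of adverse events and new SAEs stops 48 to 72 hours after the Period C dose with no later contact, although Period A and B doses are followed through a washout of at least 7 days

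*Protocol*

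**What the plan says.** Section 4.7.1.2 collects adverse events from Day -1A "through the final assessment of the final treatment period". For serious events, "SAEs will be collected from the time the informed consent is signed through final assessment of the final treatment period".

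Section 3.1 fixes when that is: "Volunteers will be discharged from the study after completion of the final blood sample and all safety assessments are completed on Day 4C". If simvastatin is the last drug, discharge and its safety assessments move to Day 3C, after the 48-hour sample. Table 1 schedules nothing after that discharge.

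The earlier periods are handled differently. Footnote g of Table 1 states: "Adverse events and concomitant medication use should be solicited upon return to the CRC after washout". Chemistry, haematology, urinalysis and serum pregnancy tests are then repeated on Day -1 of the next period.

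Three other places bear on the point:

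- The SAE definition in Section 4.7.1.1 lists follow-up as one of the study phases. The study plan has no such phase.
- Section 8.3 requires that "the outcome of all pregnancies (spontaneous miscarriage, elective termination, normal birth or congenital abnormality) must be followed up and documented".
- Section 1.1.1 says that the terminal half-life "of rosuvastatin is approximately 19 hours". Appendix D says of atorvastatin that "the half-life of inhibitory activity for HMG-CoA reductase is 20 to 30 hours due to the contribution of active metabolites".

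**The concern.** The same three drugs at the same doses are given in every period, but how long a volunteer is observed after a dose depends on the period. A Period A or B dose is followed by a week or more at home, a question about events and medication, and a fresh set of laboratory tests. A Period C dose is followed by two or three in-patient days and then nothing.

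Safety and tolerability is a stated secondary objective, and Section 6.2.1.1 summarises safety by medication and ethnic group. A muscle, liver or other event that first appears several days after the Period C dose, or an SAE in that time, would be neither solicited nor within the collection period. The last pregnancy test is drawn on the day of discharge. A pregnancy that begins around the Period C dose has no later scheduled point at which it would come to light, so the Section 8.3 duty might never be triggered.

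**Working it through.** **1. Does the schedule leave any time after Period C?** Inputs: three in-patient periods of 5 days, washouts of at least 7 days, and a stated study length of 29 days (Synopsis).

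3 × 5 + 2 × 7 = 29 days. This reproduces the stated length and leaves 0 days after Period C.

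**2. Is any later laboratory sample budgeted?** Table 5 lists 5 chemistry/serum pregnancy samples. The ticks in Table 1 give screening, Days -1A, -1B and -1C, and the Period C discharge: 5. All are used up.

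**3. How long is a volunteer observed after each dose?** Count Day -1A as study day 1 and use the minimum washout:

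- Day 1A = day 2, Day 4A = day 5, washout = days 6 to 12, Day -1B = day 13.
- Day 1B = day 14, Day -1C = day 25, Day 1C = day 26, Day 4C = day 29.

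| Dose given in | Dose to the next or last planned AE question and safety laboratory tests |
|---|---|
| Period A | 13 − 2 = 11 days |
| Period B | 25 − 14 = 11 days |
| Period C, rosuvastatin or atorvastatin | 29 − 26 = 3 days |
| Period C, simvastatin | 2 days |

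After simvastatin in Period A or B the figure is 10 days if the washout is counted from the Day 3 discharge. The Period C window is thus 3/11 = 27% of the earlier one (2/10 = 20% for simvastatin).

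**4. How many doses?** About 90 volunteers × 3 doses = 270, of which about 90 (one in three) are Period C doses. Each drug comes last in exactly one of the three sequences, so this is about 30 doses per drug if the sequences are of equal size.

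**5. How much drug is left at 72 hours?** Half-lives elapsed = 72/t½; fraction left = 0.5^(72/t½). This assumes first-order decline at the quoted mean half-life.

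| Quantity | t½ (h) | Half-lives at 72 h | Left | 4 × t½ (h) | 5 × t½ (h) |
|---|---|---|---|---|---|
| Rosuvastatin | 19 | 3.79 | 7.2% | 76 | 95 |
| Atorvastatin parent | 14 | 5.14 | 2.8% | 56 | 70 |
| Atorvastatin inhibitory activity, lower | 20 | 3.60 | 8.2% | 80 | 100 |
| Atorvastatin inhibitory activity, upper | 30 | 2.40 | 19.0% | 120 | 150 |

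Measured against five half-lives, the 72-hour close is 23 h short for rosuvastatin and 28 to 78 h short for atorvastatin inhibitory activity. Against four, it is 4 h and 8 to 48 h short. Atorvastatin parent drug is covered either way. The documents give no half-life for simvastatin, so no figure can be computed. Appendix E reports only that total radioactivity fell to about 10% of peak by 12 hours.

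**The case against.** The strongest reply is that this is a single-dose study of marketed statins whose risk Section 3.2.2 calls minimal, that safety is a descriptive secondary objective, and that the 7-day interval is a crossover washout which no section presents as a safety standard. No section sets a four- or five-half-life rule either. All of this is true. It limits the weight of the point but does not explain why the last dose should be observed for about a quarter of the time given to the others.

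Several stronger readings are tempting, and the documents do not support them:

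- *The discharge laboratory results cannot be read or recorded.* The samples are drawn within the window, Section 4.7.1.1 counts abnormal results as possible adverse events, Section 6.2.1.2 lists all laboratory data with deviations flagged, and other significant events are identified while the study report is prepared. Nothing bars a late result. What is missing is a sentence saying so, and any planned review after discharge.
- *An ALT rise first seen at discharge fails a study criterion.* The requirement in Section 1.1.4 for two or more occasions is background on the rosuvastatin programme, not a rule of this study.
- *SAE follow-up ends.* Only the collection of new SAEs ends. Section 4.7.1.3 requires follow-up information on known SAEs with no end date, and Section 8.3 continues for known pregnancies.
- *Under-reporting would be biased between drugs.* Each drug is last in one sequence, and randomisation is within ethnic group. The short window is spread evenly, apart from 48 against 72 hours for simvastatin.
- *Section 4.7.1.2 contradicts footnote g.* It does not. Footnote g governs the washouts between periods and has no counterpart after Period C.

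On pregnancy, volunteers are in-patients from Day -1C, and women of childbearing potential must abstain or use an effective method of contraception. The residual risk is small and cannot be quantified from the protocol. Finally, Figure 1 and the text of Section 5.6 are not in the copy at hand, but Table 1, Table 5 and the 29-day total all agree that no later contact is planned.

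**Conclusion.** The point holds as a gap in the safety collection window. Collection of adverse events and new SAEs closes 72 hours after the Period C dose (48 hours after simvastatin), against about 10 to 11 days to the next planned question and laboratory tests after a Period A or B dose. About 90 of 270 doses are affected, roughly evenly across drugs. The day counts assume the minimum washout.

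The pharmacokinetic support is partial. It applies to rosuvastatin (about 7% left) and to atorvastatin inhibitory activity (about 8 to 19% left), but not to atorvastatin parent drug, and it cannot be assessed for simvastatin. Calling these amounts incomplete elimination rests on a four- or five-half-life convention that the protocol does not state. The difference between periods does not depend on that convention.

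The consequence is that new late events, or a pregnancy conceived around the Period C dose, have no scheduled detection point. The primary pharmacokinetic comparison is untouched. The change is worth making because it is cheap and specific, not because the safety summary would otherwise be unusable.

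**What to change.** Reconcile Section 3.1, Table 1 with its footnotes, the SAE definition in Section 4.7.1.1 and Section 4.7.1.2, so that the follow-up phase named in the definition exists in the plan:

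- Keep collection of adverse events and SAEs open after the Period C dose for the interval already used after Periods A and B, that is, the washout of at least 7 days.
- Close it with one telephone contact that asks about adverse events, medication and pregnancy, and add that contact to Table 1 and to the stated study length.
- State that abnormal results from samples drawn at the Period C discharge fall within the collection window even if reported later. Any repeat testing or management stays with the investigator.

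The cost is one call for each of about 90 volunteers and last-subject-out about one week later. Dosing, sample size, blood volume and the pharmacokinetic analysis do not change.
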